7.1.1.2 Frequency of tumor re-evaluation

The baseline disease evaluation by tumor imaging as outlined in [Table 4](#) should be performed within 12 weeks prior to randomization date. Scans performed as part of routine clinical management are acceptable for use as the screening scan if they are of diagnostic quality and performed within 12 weeks prior to the randomization date.

Evaluation for tumor recurrence will be performed through contrast-enhanced chest and upper abdomen CT scan to be performed every 12 weeks (+/- 2 weeks) during the 1st year after randomization, every 6 months (+/- 4 weeks) for the 2nd and 3rd year, yearly (+/- 4 weeks) for year 4 and 5. Thereafter, the imaging work-up should be performed at least yearly up to year 10. The imaging schedule takes as reference the start date of treatment (C1D1) and is not adjusted for delays in treatment. Imaging needs to be based on calendar and not adjusted for delays in treatment.

7.1.1.3 Date of recurrence

This is defined as the first day when the RECIST version 1.1 criteria for disease recurrence are met.

The first date when recurrence was observed is taken into account regardless of the method of assessment. Therefore recurrence will be declared for any lesion when:

- ◆ Only imaging was performed and progression confirmed;
- ◆ Only pathology was done and malignancy confirmed (in solitary or in doubtful lesions, cutaneous, subcutaneous or lymph node lesions);
- ◆ Both pathology and imaging were done and progression/malignancy confirmed. In this case, whatever examination came first its date is considered the date of recurrence.

7.1.2 Disease free survival (DFS)

Definition of date of disease recurrence is given above (see [Section 7.1.1.3](#)). Recurrence of disease can be a loco-regional recurrence, a distant (metastatic) recurrence or a second primary. NSCLC and second malignancies will be considered to be events.

Disease Free Survival (DFS) is calculated as the time from randomization to either the date of disease recurrence or the date of death (whatever the cause). The date of first documented disease recurrence (if applicable) will be used as the date of event. Patients alive with no evidence of disease recurrence at the time of their last visit are censored at the time of the last examination.

7.1.3 Overall survival (OS)

Overall survival (OS) is defined as the time from the date of randomization to the date of death, whatever the cause. The follow-up of patients still alive will be censored at the moment of last visit/contact.

7.1.4 Lung Cancer Specific Survival (LCSS)

Lung Cancer Specific Survival (LCSS) is calculated as the time from randomization to the date of death (due to lung cancer specifically). The follow-up of patients still alive will be censored at the moment of last visit/contact. Patients who die from causes other than lung cancer are censored at the time of death.

7.2 Evaluation of safety

7.2.1 Adverse events

All adverse events will be recorded as specified below in the protocol; the investigator will assess whether those events are drug related (reasonable possibility, no reasonable possibility) and this assessment will be recorded in the database for all adverse events.

All adverse events must be followed until resolution or stabilization.

7.2.2 General evaluation of adverse events

This study will use the International Common Terminology Criteria for Adverse Events (CTCAE), version 4.03, for adverse event reporting. A copy of the CTCAE can be accessed from the EORTC home page <https://www.eortc.be/services/doc/ctc/>.

Hematological toxicity will be assessed on the basis of regular blood tests. The nadir count will be computed at each study medication administration and graded according to the CTCAE version 4.03.

Non hematological acute side effects will be assessed and reported separately for each study medication administration, and graded according to the CTCAE version 4.03.

Planned safety analysis and tabulations are described in the statistics Chapter 8.

7.2.3 Serious adverse events

Serious adverse events are defined by the Good Clinical Practice Guideline.

**SERIOUS ADVERSE EVENTS SHOULD BE IMMEDIATELY REPORTED
ACCORDING TO THE PROCEDURE DETAILED IN THIS PROTOCOL** (see
Chapter on Reporting Serious Adverse Events)

**For guidance regarding Events of Clinical Interest (ECI) for pembrolizumab please
refer to [Appendix I](#).**

7.2.4 Toxic deaths

Toxic death is defined as death due to toxicity (defined as a serious adverse events at least with reasonable possibility to be related to study treatment). The cause of death must be reported as "toxicity" and as a serious adverse event. The evaluation of toxic deaths is independent of the evaluation of response (patients can die from toxicity after a complete assessment of the response to therapy).

7.2.5 Evaluability for safety

All patients who have started the treatment will be included in overall safety analyses.

Patients who have discontinued treatment because of toxicity will always be included in the safety analyses.

8 Statistical considerations

8.1 Statistical design

8.1.1 Sample size considerations

The primary endpoints are disease free survival (DFS) in all patients and in a subgroup of patients with **PD-L1 strong positive (tumor proportion score (TPS) \geq 50%)**.^{CCI}

Assumptions for the sample size calculation:

^{CCI} [REDACTED] The study is designed with primary/dual-primary endpoints: DFS in the whole population and DFS in the PD-L1 strong positive sub-population. Assumptions and the testing strategy are given below.

- ◆ Overall, an improvement of 14 months in median DFS (from 42 months to 56 months) or equivalent to HR = 0.75 is aimed for the whole population.^{CCI}
- [REDACTED]
- [REDACTED] The enrollment duration is 52 months with the accrual rates provided in [Table 7](#) below.
- ◆ The yearly drop-out rate is 2.5% and 1% for DFS and OS, respectively.

[figure not shown]
Table 7. Enrollment Pattern

Period	Starting at time	Calendar Time	Accrual Rate
1	0	January 2016	8.375
2	8	September 2016	18
3	26	March 2018	34.24
4	47	December 2019	13.992

[figure not shown]
- ◆ The family-wise error rate (Type I error) for DFS and OS hypotheses is strongly controlled at 2.5%, one-sided. The study uses the graphical method of Maurer and Bretz [Ref. 75] to provide strong multiplicity control for multiple hypotheses as well as interim efficacy analyses. See Figure 3 for an overview of the multiplicity strategy.
- ◆ CCI [REDACTED] The schedule and type of analyses for DFS and OS are given in Table 8 and Table 9, respectively.
- ◆ A Hwang-Shih-DeCani (HSD) spending function with $\gamma = -4$ is used to establish the boundary (nominal alpha) in interim and final analysis of DFS and OS for the test of each population. The threshold alphas and HRs for each analysis can be found in Table 8 and Table 9.
- ◆ All DFS analyses are DFS event-driven. The timing for interim analysis 1 and 2 will be determined by the number of DFS events in the PD-L1 strong positive population, CCI [REDACTED]
- ◆ CCI [REDACTED]

Approximately 1180 participants will be randomized in a 1:1 ratio into the experimental arm and the control arm. CCI [REDACTED]

[REDACTED] If either of the tests for the primary endpoints is significant, then the study can be declared successful in the respective population. Table 8 and Table 9 summarize the power to reject the null hypotheses for DFS and OS and their corresponding individual hypotheses at the different times of analyses.

CCI

CCI

CCI

8.1.2 Randomization and stratifications

All patients entered will be centrally registered at the EORTC Headquarters (for practical details, see Chapter on randomization procedure). The Pocock and Simon Minimization with Biased-coin Assignment methodology [Ref. 73] will be utilized to perform subject randomization for this study. Per suggestion of the ICH E9 statistical guidelines, the algorithm has been modified to incorporate a random allocation component in order to ensure 15% of completely random assignments. Stratification factors are: stage (IB vs II vs IIIA), adjuvant chemotherapy (no adjuvant chemotherapy versus adjuvant chemotherapy), PD-L1 status: negative (TPS=0%) versus weak positive (TPS = 1-49%) - versus strong positive (TPS≥50%) and regions (Western Europe versus Eastern Europe versus Rest of the world versus Asia). Minimization algorithm separately applied for each PD-L1 status, to ensure an optimal balance of treatment arms within each PD-L1 level.

Treatment allocation will be blinded (see Chapter 14).

Note: Tumor staging is based on TNM stage (according to the 7th edition of the TNM classification for lung cancer).

8.2 Statistical analysis plan

8.2.1 Primary/dual-primary and secondary endpoints

The primary/dual-primary endpoints and all secondary endpoints are defined in Chapter 7. Technical derivation of these endpoints using the case report forms(CRFs) is included in [Appendix N](#).

8.2.2 Analysis populations

- ◆ Intention-to-treat population: All randomized patients will be analyzed in the arm they were allocated by randomization.
- ◆ Safety population: All patients who have started their allocated treatment (at least one infusion of the study drug(s))

These populations are also applicable to the predefined PD-L1 subgroups.

8.2.3 Statistical methods

8.2.3.1 Efficacy endpoints

The primary analyses of the primary and secondary efficacy endpoints (DFS, OS and LCSS) will be performed on all randomized patients according to the intention to treat (ITT) principle.

Estimates and confidence intervals

Estimates of the median DFS, OS and LCSS will be obtained by the Kaplan Meier technique. The 95% confidence interval (CI) for the median will be calculated using the reflected CI method.

Estimates of the event-free rate at a fixed time point will be obtained using the Kaplan Meier technique and 95% CI will be calculated by the Greenwood's formula for standard deviation. Estimates of hazard ratios and their 95% CI will be obtained by Cox regression. Kaplan Meier curves will be drawn for both the experimental and control arms on the same plot.

Inference

The DFS and OS will be analyzed by a Cox Proportional Hazard Regression with treatment adjusted by the following covariates: stratification factors including stage, PD-L1 IHC expression, adjuvant chemo, regions, and additional factors including histology and smoking status. Permutation test [Ref. 74] will be used as a primary test for DFS to compare the experimental versus the control arm. The Wald test without permutation of allocation sequence will be used as a supportive analysis for DFS, but as a primary test for OS. The hazard ratios and corresponding 95% CIs will be estimated using the multivariate Cox regression model stated above (using Efron's tie-handling method). A sensitivity analysis will include sex (male vs. female) and age (<65 vs. ≥ 65 years) as additional adjustment factors in the Cox regression model. A logrank test with no adjustment factors to compare the two arms will also be performed as a sensitivity analysis.

If a randomized patient is not disease free at baseline, the date of randomization will be used as the date of event for the primary DFS analysis in the PD-L1 strong positive, PD-L1 positive and the whole population.

Analysis of LCSS will be based on the log-rank test and Cox regression model. Competing risks approaches such as cumulative incidence function (CIF), Gray's test, Fine-Gray subdistribution hazard model, etc., will also be performed, where deaths from other causes are considered as competing risks. As no Type I error control is applied to LCSS, the p-values for LCSS analyses, if provided, are nominal only and for descriptive purpose.

Table 10. Analysis Strategy for Key Efficacy Variables

Endpoint/Variable (Description, Time Point)	Primary vs. Supportive Approach†	Statistical Method‡	Analysis Population	Missing Data Approach
Primary/dual-primary Endpoints				
DFS	P	Permutation test with multivariate Cox regression model§	ITT ◆ all patients, ◆ PD-L1 strong positive ◆ PD-L1 positive	Model-based
	S	Wald test in multivariate Cox regression model Non-adjusted logrank test	ITT ◆ all patients, ◆ PD-L1 strong positive ◆ PD-L1 positive	Model-based
Secondary Endpoints				
OS	P	Wald test in Multivariate Cox regression model	ITT ◆ all patients, ◆ PD-L1 strong positive ◆ PD-L1 positive	Model-based
LCSS	P	Non-adjusted logrank test	ITT ◆ all patients,	Model-based
† P=Primary approach; S=Secondary approach. ‡ Statistical models are described in further detail below: § Adjusted by Stage (IB versus II versus IIIA), PD-L1 IHC expression (0 versus 1-49% versus ≥ 50%), Adjuvant Chemo (No chemotherapy vs. adjuvant platinum-based chemotherapy), Histology (squamous vs. non-squamous), smoking status (smokers vs. non-smokers), and regions (Western Europe versus Eastern Europe versus Rest of the world versus Asia).				

The strategy to address multiplicity issues with regard to multiple endpoints and interim analyses is described in Section 8.3, Interim Analyses and in the below subsection on Multiplicity.

[figure not shown]

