1.1 Early stage Non Small Cell Lung Cancer

Lung Cancer is the leading cause of cancer-related death world-wide; in 2012, 313,000 new cases have been estimated in Europe and 1,825,000 worldwide with 268,000 and 1,590,000 deaths respectively [Ref. 1, Ref. 2].

Non Small Cell Lung Cancer (NSCLC) accounts for 80-85% of all lung cancers, about 20% of cases being diagnosed at an early stage when the disease is still curable by surgery.

The most common histological subtypes of NSCLC include adenocarcinoma, squamous cell carcinoma (SqCC), and large-cell carcinoma (LCC). Immunohistochemistry is often helpful in distinguishing between these subtypes; SqCCs is usually TTF-1-negative and p63-positive, whereas adenocarcinomas are often TTF-1-positive. This differentiation can dictate treatment management in the advanced stage but not for surgery or adjuvant chemotherapy [Ref. 3].

Age, performance status (PS) and stage are the main prognostic factors in early stage NSCLC. Gene sequencing studies in early-stage NSCLC have reported prognostic signatures, but no signatures have been prospectively validated in independent studies. The use of biomarkers predicting adjuvant chemotherapy efficacy has recently been evaluated in the LACE bio group without strong recommendations for further studies [Ref. 4].

Surgical resection is the standard treatment for operable patients with resectable stage I to IIIA [Ref. 5, Ref. 6].

The surgical procedure used depends on the extent of the disease and on the cardiopulmonary reserve of the patient. Lobectomy or pneumonectomy with lymphadenectomy are the main options according to the location and size of the tumor, age, performance status (PS), general comorbidities and lung function of the patient [Ref. 7]. Video-assisted thoracoscopic surgery (VATS) may be an alternative to thoracotomy for patients undergoing lobectomy [Ref. 8]. This is a minimally invasive approach that decreases surgical morbidity, including perioperative pain, and is particularly useful for those with significant medical comorbidities [Ref. 9]. Although the efficacy of VATS compared to conventional surgical techniques has not been definitively established, several large case series support the safety and efficacy of this technique for patients with stage I NSCLC [Ref. 10, Ref. 11, Ref. 12].

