3.3.2 Patient status

- ◆ ECOG Performance status 0-1;
- ◆ Adequate organ function performed within 10 days of treatment initiation and defined as follows:

Table 3. Adequate Organ Function Laboratory Values

System	Laboratory Value
Hematological	
Absolute neutrophil count (ANC)	$\geq 1,5 \times 10^9/L$
Platelets	$\geq 100 \times 10^9/L$
Hemoglobin	$\geq 9 \text{ g/dL}$ or $\geq 5.6 \text{ mmol/L}$
Renal	
Creatinine OR Measured or calculated creatinine clearance (GFR can also be used in place of creatinine or CrCl)	$\leq 1.5 \times \text{ULN}$ OR $\geq 30 \text{ mL/min}$ for subject with creatinine levels $> 1.5 \times$ institutional ULN

System	Laboratory Value
Hepatic	
Total bilirubin	$\leq 1.5 \times \text{ULN}$ OR Direct bilirubin $\leq \text{ULN}$ for subjects with total bilirubin levels $> 1.5 \times \text{ULN}$
AST (SGOT) and ALT (SGPT)	$\leq 2.5 \times \text{ULN}$
a Creatinine clearance should be calculated per institutional standard.	
b. For patients with Gilbert's disease total bilirubin may be $> 1.5 \times \text{ULN}$, however direct bilirubin must be normal	

- ◆ Adjuvant chemotherapy is not mandatory but considered for patients with stage IB (T ≥ 4 cm) and strongly recommended for stage II and IIIA, and will be administered according to national and local guidelines. Patients who received more than 4 cycles of adjuvant therapy are not eligible;
 - ◆ Patients not receiving adjuvant chemotherapy must be randomized and dosed with pembrolizumab/placebo within 12 weeks of their surgery date.
 - ◆ Participants who receive adjuvant chemotherapy must begin adjuvant chemotherapy within 12 weeks of their surgery date. Patients receiving adjuvant chemotherapy must be randomized and dosed with pembrolizumab/placebo at least 3 weeks but no more than 12 weeks from the last dose of chemotherapy (Day 1 of last cycle).
- ◆ No prior or planned neoadjuvant or adjuvant radiotherapy and/or neoadjuvant chemotherapy for the current malignancy is allowed; No prior treatment with anti-PD-1, anti-PD-L1/2, anti-CD137, CTLA-4 modulators or any other immune-modulating agents; patients receiving live vaccine within 30 days prior to the first infusion of study treatment are not eligible;
- ◆ No current participation in an interventional clinical trial or treatment with an investigational agent or use of an investigational device within 4 weeks of the first infusion of study treatment;

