6.2.1 Within 12 weeks prior to randomization

The patient's written informed consent ('Main Study') to undergo screening for the clinical trial must be given prior to the performance of any protocol laboratory/imaging tests (that are not part of local routine guidelines) and collection of HQRoL,.

Upon confirmation of the PD-L1 status and ('Main Study') written informed consent, the following exams will be performed during the screening phase (maximum of 12 weeks from ICF signature until the randomization) and results must be known before randomization:

- ◆ Eligibility criteria (see Section 3.3);
- ◆ Demographics, medical history, height and smoking status;
- ◆ HIV, HBV, HCV serology (Active Hepatitis B is defined as a known positive HBsAg result. Active; active Hepatitis C is defined by a known positive Hep C Ab result and known quantitative HCV RNA results greater than the lower limits of detection of the assay) if clinically indicated according to the local investigator;
- ◆ Physical examination (including heart rate, blood pressure, weight and temperature);
- ◆ ECOG performance status (see Appendix C);
- ◆ Urinalysis (specific gravity, pH, proteins, glucose, blood using a dipstick; elements and microscopic examination if needed);
- ◆ Thyroid function: TSH; in case of elevated TSH to add free T3 and T4;
- ◆ Cardiac function: 12-lead ECG;
- ◆ Disease evaluation : the following imaging work up must be performed:

- ◆ Contrast-enhanced chest and upper abdomen CT scan;
- ◆ Contrast-enhanced brain CT scan or MRI;
- ◆ Concomitant medications assessment;
- ◆ Adverse event assessment;
- ◆ HRQoL evaluations : EORTC QLQ-C30 version 3, EORTC QLQ-LC13 and EQ-5D;

Please refer to [Table 4](#) in Section [6.8.1](#).

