8.2.4 Pre-planned sensitivity or exploratory analyses

In addition to the analyses mentioned in the previous section, the following sensitivity analyses may also be performed:

- ◆ using the ITT population, but considering the stratification factor - Stage (AJCC V7) information as indicated on the CRFs based on pathology report(s). Stage information based on AJCC V8 converted from AJCC V7 and additional information collected in the database may also be considered.
- ◆ For the randomized patient not disease-free at baseline, the date of randomization is used as the censoring date for DFS analysis.

- ◆ Proportional hazard assumption will be checked. If the data clearly do not follow proportional hazards, medical explanations should be identified and alternative statistical methods will be explored.
- ◆ Sensitivity analyses for DFS may also be conducted, adjusted by complete resection status (complete resection vs. uncertain) as assessed and described by the quality assurance for surgery [Ref. 86].

Subgroup analyses are planned to compare DFS by treatment arm in the stratification factors. In addition, subgroup analyses by histology, smoking status, sex and age are also planned. Two cut-off values for age (70 years and 75 years) to define elderly population will be explored to assess the impact of geriatric domains on study primary/dual-primary endpoints and PD-L1 status. Subgroup analyses by complete resection status (complete resection vs. uncertain) as assessed and described by the quality assurance for surgery [Ref. 86] may also be conducted.

The above analyses will be repeated for the secondary endpoint OS.

Exploratory analysis: factors related to the cure rate

Cure rate, defined as proportion of patients who are still alive when the OS curve reaches plateau- will be explored. Any conclusion on cure rate should incorporate all subgroups (mature and less mature observations with respect to the terminal plateau) and consistency check will be performed to examine subgroups with less mature observations if the same conclusion can be drawn for those subgroups.

Proportion of PD-L1 status

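### The primary DFS and OS models leave out age and ECOG PS, which the protocol counts among its main prognostic factors: a small missed gain in power, not an error

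*Combined protocol and SAP*

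**What the plan says.** Section 8.2.3.1 analyses DFS and OS by Cox regression with treatment adjusted for "stratification factors including stage, PD-L1 IHC expression, adjuvant chemo, regions, and additional factors including histology and smoking status". The Table 10 footnote repeats the six covariates with their levels. DFS is tested primarily by a permutation test based on this model, and OS by its Wald test.

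Section 1.1 states: "Age, performance status (PS) and stage are the main prognostic factors in early stage NSCLC". Of these three, only stage is in the primary model. Section 8.1.2 does not list age or PS among the minimisation factors.

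Age enters elsewhere. Section 8.2.3.1 says: "A sensitivity analysis will include sex (male vs. female) and age (<65 vs. ≥ 65 years) as additional adjustment factors". Section 8.2.4 adds that "subgroup analyses by histology, smoking status, sex and age are also planned", explores cut-offs at 70 and 75 years, and repeats these analyses for OS. ECOG PS is named in no efficacy model or subgroup analysis in Section 8.2, and Section 8.2.5 foresees no further prognostic factor analyses.

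Both variables are available. Section 3.3.2 makes "ECOG Performance status 0-1" an eligibility criterion. Section 6.2.1 collects "Demographics, medical history, height and smoking status" and assesses ECOG PS at screening. Section 14.4 asks for date or year of birth at randomization. The plan does not explain why histology and smoking were added to the stratification factors while age and PS were not.

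**The concern.** In a Cox model, leaving out a covariate that predicts outcome pulls the estimated treatment hazard ratio toward 1 and lowers power, even when the covariate is balanced between arms. Here the plan has already chosen covariate adjustment for its confirmatory tests, and it names the factors it regards as most prognostic. It then leaves two of the three out of the primary model, although the data will be in hand for every patient.

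The stake is some power for the dual-primary DFS tests and for OS. A second, lesser stake is that a chance imbalance in PS would not be adjusted for in any analysis that Section 8.2 names.

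**Working it through.** **Inputs from the documents.** Whole-population DFS: median 42 to 56 months, HR 42/56 = 0.75 (Section 8.1.1). 551 events, with about 86% power at one-sided 1.25% and about 92% at 2.5% (protocol summary, number of patients). 1180 patients, 1:1, 2.5% yearly DFS drop-out. Table 7 accrual: 8×8.375 + 18×18 + 21×34.24 + 5×13.992 = 1180.

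**Step 1: reproduce the stated power.** Schoenfeld: power = Φ(√(551/4) × |ln 0.75| − z). The first term is 11.737 × 0.2877 = 3.376.
- One-sided 1.25%: Φ(3.376 − 2.241) = 87.2%.
- One-sided 2.5%: Φ(3.376 − 1.960) = 92.2%.

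With Hwang-Shih-DeCani spending (γ = −4) and assumed interim looks between 60% and 85% information (the real fractions are redacted), power is 86.3–86.8% and 91.6–91.8%. The stated figures hold. They rest on events and HR alone and claim no gain from covariates.

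**Step 2: size of the gain.** The documents give no prognostic strength for age or PS, so these are assumptions: 50% of patients aged 65 or over, 40% ECOG 1, and the same hazard ratio for each factor, varied from 1.2 to 2.0. The check used 5,000 simulated trials per scenario with the accrual and drop-out above, exponential DFS with control median 42 months, a conditional treatment HR of 0.75 and a cut at 551 events. It compared a Cox model with treatment only against one with treatment, age and PS. Power is Φ(mean Z − z). The saving in events is 1 − (Z without / Z with)². Gains are from unrounded values.

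| HR of each factor | Estimated HR without / with | Mean Z without / with | Power at 1.25% | Gain | Power at 2.5% | Gain | Events saved |
|---|---|---|---|---|---|---|---|
| 1.2 | 0.750 / 0.749 | 3.350 / 3.369 | 86.6 / 87.0% | 0.4 | 91.8 / 92.1% | 0.3 | about 1% |
| 1.3 | 0.751 / 0.749 | 3.330 / 3.368 | 86.2 / 87.0% | 0.8 | 91.5 / 92.0% | 0.6 | about 2% |
| 1.5 | 0.755 / 0.749 | 3.281 / 3.368 | 85.1 / 87.0% | 1.9 | 90.7 / 92.0% | 1.4 | about 5% |
| 2.0 | 0.765 / 0.749 | 3.129 / 3.370 | 81.3 / 87.1% | 5.8 | 87.9 / 92.1% | 4.2 | about 14% |

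Counting rejections directly at 1.25% gives gains of 0.3, 0.6, 2.3 and 5.7 points, with Monte Carlo standard errors of 0.2, 0.2, 0.3 and 0.4.

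**Step 3: a second set of assumptions.** Take PS 1 in 36% of patients and age continuous with SD 9 years. The attenuated HR from a treatment-only model was put into the Schoenfeld formula at 551 events and one-sided 1.25%, against 87.2% adjusted.
- PS 1.2, age 1.1 per 10 years: 87.1%, gain 0.1 points.
- PS 1.4, age 1.2: 86.5%, gain 0.7.
- PS 1.6, age 1.3: 84.9%, gain 2.3.
- PS 1.8, age 1.4: 83.1%, gain 4.1.

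**Step 4: chance imbalance in PS.** If 40% are PS 1, the 95% range for the between-arm difference is ±1.96 × √(0.4 × 0.6 × 4/n). That is about ±5.6 points for n = 1180 and ±10.5 for the roughly 334 strong-positive patients in the protocol summary. A 10.5-point imbalance with a PS hazard ratio of 1.5 moves an unadjusted treatment HR by about 0.105 × ln 1.5 = 0.043 on the log scale, or 4%. This is ordinary random error, not bias, but adjustment would remove it.

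**What was not computed.** Both power checks used a treatment-only comparator and not the planned six-covariate model. They used Wald or Schoenfeld power and not the permutation test. The strong-positive and OS event numbers are redacted, so those gains were not calculated.

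**The case against.** The case for leaving the plan alone is a fair one.

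- **No figure is wrong.** A reader might infer that the trial is underpowered, or that the 86% and 92% are overstated. The documents do not support that. The design HR of 0.75 is defined through population medians without reference to covariates. Read that way, the planned test keeps its stated power and adjustment only adds to it. Taking 0.75 as the conditional HR, as in the working, is a modelling choice.
- **Age is not ignored.** It has a pre-specified sensitivity model and several subgroup analyses, so an imbalance in age would be seen. Only ECOG PS is wholly absent. The sensitivity model cannot carry the confirmatory test, however.
- **The gain may be smaller than shown.** If age and PS overlap with included covariates, such as receipt of adjuvant chemotherapy, part of their information is already used. Entry is limited to completely resected, disease-free patients with ECOG 0–1, which narrows the range of PS. Section 1.1 is a general background statement and does not show that either factor is strong here.
- **Changing the model mid-trial is not free.** DFS and OS are tested group-sequentially, and a different model between looks would change the statistic to which the boundaries apply.

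All four points stand, and they limit the size and the timing of the change. They do not explain why factors that the protocol ranks with stage are left out of models that already adjust for six others.

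**Conclusion.** The point holds as a low-cost improvement. The confirmatory DFS and OS models omit two recorded factors that the protocol itself ranks with stage, and ECOG PS is in no efficacy analysis named in Section 8.2. The power statement is correct and type I error is not affected.

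For whole-population DFS, measured against a treatment-only model, the gain at one-sided 1.25% is probably under 1 point if each factor has a hazard ratio up to about 1.3, and about 2 points at 1.5. It reaches 4 to 6 points only for strong effects. All of this rests on assumed prevalences and prognostic strengths. It would be tempting to carry these figures over to OS and to the PD-L1 strong-positive subgroup, but with their event numbers redacted only the direction can be stated.

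**What to change.** In Section 8.2.3.1 and the Table 10 footnote, add ECOG PS (0 versus 1) and age (continuous, linear) to the covariates of the primary DFS and OS models. Drop the 65-year age cut from the sensitivity model, where it becomes redundant, and keep sex there.

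Blinded staff should make the change. It should apply only to hypotheses not yet tested at an unblinded look. For any hypothesis already tested, keep the current model as primary and use the expanded model as a pre-specified sensitivity analysis.

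The cost is a SAP amendment and two degrees of freedom. From the Table 10 levels the current covariates use 2 (stage) + 2 (PD-L1) + 1 (chemotherapy) + 1 (histology) + 1 (smoking) + 3 (region) = 10, so the total becomes 12 plus treatment, against 551 DFS events in the whole population. No new data are needed.
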